8.11	DATA SAFETY AND MONITORING BOARD REVIEW	64
8.11.1	Routine DSMB Reviews	64

8.11.2	Protocol-Defined Interim Safety Reviews	64
8.11.3	Ad hoc DSMB Reviews (Stopping Rule Guidance)	65
9. S	TATISTICAL CONSIDERATIONS AND ANALYTICAL PLAN	66
9.1	ANALYSIS SAMPLES	66
9.1.1	Analysis Populations	66
9.2	ANALYSIS OF ENDPOINTS	66
9.2.1	Primary Endpoint	66
9.2.2	Secondary and Exploratory Endpoints	66
9.2.3	Analysis of Dose-Response Relationship	68
9.2.4	Missing Data	68
9.2.5	Baseline Characteristics and Demographics	68
9.2.6	Safety Analysis	68
9.2.7	Interim Analysis of Safety Data	69
9.2.8	Medical History	69
9.2.9	Use of Medications	69
9.3	SAMPLE SIZE	69
9.4	REPORTING DEVIATIONS FROM THE ORIGINAL STATISTICAL PLAN	70
10. A	ACCESS TO SOURCE DATA/DOCUMENTS	70
11. Q	QUALITY CONTROL AND QUALITY ASSURANCE	70
12. E	THICAL CONSIDERATIONS AND COMPLIANCE WITH GOOD CLINICAL	
12.1	STATEMENT OF COMPLIANCE	
12.2	INFORMED CONSENT	71
12.3	PRIVACY AND CONFIDENTIALITY	72
13. P	PUBLICATION POLICY	72
	REFERENCES	
Liozo	F APPENDICES	
		70
APPEN	NDIX 1. Schedule of EventsNDIX 2. Clinical Criteria For Diagnosing AnaphylaxisNDIX 3. Examples of Strong CYP3A4 Inhibitors, inducers, and P-gp inhibitors	79
LIST O	F TABLES	
Table 2	1 Attribution of Adverse Events	69
Table 3	3 Confidence Limits	70

LIST OF FIGURES	
Figure 1. Study Schema	33

SYNOPSIS

Title Evaluation of Brentuximab Vedotin for Diffuse Cutaneous Systemic

Sclerosis: A Phase 1/2 Multicenter Randomized, Double Blinded,

Safety Study

IND Sponsor DAIT NIAID

Conducted by Immune Tolerance Network

Protocol Chair(s) [name] and [name]

Accrual Objective 24 participants who receive sufficient doses of the investigational

medication to assess safety

Study Treatment Three ascending dose cohorts will receive brentuximab vedotin or placebo

equivalent

Study Design This trial will be conducted as a multicenter prospective double blind

placebo-controlled dose escalation safety study with brentuximab vedotin and stable background immunosuppressive therapy in adult individuals with dcSSc. Adult male and female participants with dcSSc will be recruited by a

collaborative group of clinical sites in the United States.

[figure not shown]
Participants who meet the eligibility criteria will be enrolled without regard to gender, race, or ethnicity. Eligible participants will be randomly assigned to study treatment, either brentuximab vedotin or placebo equivalent in a 6:2 ratio favoring brentuximab vedotin. Three dose cohorts are planned with 8 participants in each cohort, for a total of 24 participants who receive sufficient doses of the investigational medication to assess safety.

The doses planned for each ascending dose cohort include 0.6mg/kg, 1.2 mg/kg, and 1.8 mg/kg brentuximab vedotin or placebo equivalent. All cohorts will receive intravenous administration of study medication every 3 weeks for 21 weeks, for a total of eight doses. Following completion of treatment, participants will undergo follow-up visits at weeks 24, 28, 36 and 48.

After completion of the first 12 weeks of treatment for each of the first two cohorts of 8 participants, an interim safety analysis will be conducted and reviewed by an independent Safety Review Committee, as described in Section 8.11.2. Approval by the Safety Review Committee following the 12-week interim safety analysis will be required before proceeding to the next higher dose of brentuximab vedotin.

Interim safety analysis will also be conducted at 24 weeks following completion of study treatment for each of the first two cohorts of 8 participants. Following either the week 12 or the week 24 interim safety

reviews, the Safety Review Committee can recommend actions regarding study conduct, as described in Section 8.11.2.

Study Duration

Total study duration target is 308 weeks:

- Enrollment phase duration target is 260 weeks.
- Study participation phase for each participant is 48 weeks, which includes a treatment phase of 21 weeks and a follow-up phase of 27 weeks.

Primary Objective

To assess the safety and tolerability of brentuximab vedotin in diffuse cutaneous systemic sclerosis (dcSSc).

Primary Endpoint

The primary endpoint will be the proportion of participants who experience at least one Grade 3 or higher adverse event at or before week 48.

Secondary Endpoints

Safety Endpoints:

1. The proportion of participants who experience at least one Grade 3 or higher adverse event at or before weeks 12, 24, and 36.

- 2. The proportion of participants who experience at least one Grade 2 or higher adverse event at or before weeks 12, 24, 36, and 48.
- 3. The proportion of participants with Grade 2 or higher peripheral neuropathy at or before weeks 12, 24, 36, and 48.
- 4. The proportion of participants with Grade 3 or higher neutropenia at or before weeks 12, 24, 36, and 48.
- 5. The proportion of participants with any of the following Grade 3 or higher adverse events at or before week 48:
 - a. Peripheral neuropathy.
 - b. Neutropenia.
 - c. Infectious adverse events.
 - d. Infusion reactions, including anaphylaxis and new onset rash consistent with Stevens-Johnson syndrome, toxic epidermal necrolysis, or other drug reaction.
 - e. PML.

Exploratory Efficacy Endpoints:

- 1. Modified Rodnan Skin Score (mRSS) at weeks 12, 24, and 48
- Provisional American College of Rheumatology Combined Response Index in Systemic Sclerosis (CRISS) at weeks 24 and 48.
- 3. Percent predicted Forced Vital Capacity (FVC) at weeks 24 and 48 weeks.
- 4. Physician's global assessment on a Likert scale at weeks 24 and 48.
- 5. Patient's global assessment on a Likert scale at weeks 24 and 48.
- 6. Health-related quality of life (HRQOL) assessed by PROMIS-29 version 2.0 at weeks 24 and 48.
- Physical function assessed by the Scleroderma Health Assessment Questionnaire-Disability Index (SHAQ-DI) at weeks 24 and 48.

Inclusion Criteria

- Classification of systemic sclerosis (SSc), as defined using the 2013 American College of Rheumatology/European Union League Against Rheumatism classification of SSc.
- 2. Diagnosis of dcSSc, as defined by LeRoy and Medsger.

Immune Tolerance Network CONFIDENTIAL Page 12

- 3. Disease duration ≤ 60 months (defined as time from the first non-Raynaud phenomenon manifestation).
- 4. mRSS units \geq 15 and \leq 45, and both of the following:
 - a. At least mild skin thickening (\geq 1+ mRSS) of the forearm, and
 - b. At least moderate skin thickening (≥ 2+ mRSS) at the planned forearm skin biopsy site.
- 5. Documentation of at least 12 weeks of ongoing immunosuppressive therapy for SSc at the time of enrollment, and at least 4 weeks at a stable dose, of one of the following:
 - a. Methotrexate ≤ 25 mg/week, or
 - b. Mycophenolate mofetil ≤ 3 grams/day or mycophenolate sodium ≤ 2.16 grams/day, or
 - c. Azathioprine $\leq 3 \text{mg/kg/day}$.
- 6. Age 18-70 years inclusive.
- 7. Completion of primary SARS-CoV-2 vaccination series is required at least 14 days prior to the first infusion of study medication at Visit 0. The dose and schedule of the vaccine is defined according to current FDA approval or Emergency Use Authorization at the time of screening.
- 8. Ability to provide informed consent.

Exclusion Criteria

- 1. Rheumatic disease other than dcSSc; it is acceptable to include patients with osteoarthritis, fibromyalgia, sicca symptoms, and scleroderma-associated myopathy.
- 2. Limited cutaneous SSc or sine scleroderma.
- 3. Pulmonary disease with FVC \leq 60% of predicted, or DLCO (corrected for hemoglobin) \leq 60% of predicted.
- 4. Pulmonary hypertension (PH) or moderate to severe left ventricular dysfunction defined as one of the following:
 - a. Transthoracic echocardiography demonstrating at least one of the following (unless subsequent right heart catheterization does not demonstrate PH; or unless prior right heart catheterization within one year did not demonstrate PH and echocardiography results are not significantly changed):

- Tricuspid regurgitation jet >2.8 m/sec or estimated right ventricular systolic pressure > 42 mm Hg, or
- ii. At least one of the following:
 - Abnormality of right atrial size, shape, or wall thickness consistent with PH, or
 - Abnormality of right ventricular size, shape, or wall thickness consistent with PH, or
 - 3. Abnormal septal wall shape consistent with PH.
- Left Ventricular Ejection Fraction (LVEF) < 50%.
- b. Right heart catheterization showing mean pulmonary artery pressure ≥25 mm Hg at rest.
- c. Current use of approved medications for PH. It is acceptable to use phosphodiesterase type 5 (PDE-5) inhibitors for Raynaud's, digital ulcers, and intermittently for erectile dysfunction.
- 5. Active scleroderma renal crisis within the 4 months prior to enrollment.
- 6. History of moderate-to-severe lower gastrointestinal dysmotility such as current use of parenteral nutrition and/or recent history of intestinal pseudo-obstruction within 3 months prior to enrollment.
- 7. The following medications:
 - a. Oral corticosteroids >10 mg/day of prednisone or equivalent within 2 weeks prior to enrollment.
 - b. Treatment with intravenous immunoglobulin (IVIG) within 12 weeks prior to enrollment.
 - c. Treatment with cyclophosphamide within 6 months prior to enrollment.
 - d. Use of investigational biologic or non-biologic medication within the past 90 days, or 5 half-lives prior to enrollment, whichever is greater, except for SARS-CoV-2 vaccines, and medications used for prevention and treatment of COVID-19, per FDA Emergency Use Authorization.

- e. Use of anti-TNF medication or other biologic medications within the past 90 days, or 5 half-lives prior to enrollment, whichever is greater.
- f. Prior treatment with anti-CD20 if either of the following are true:
 - i. B cells \leq lower limit of normal (LLN), or
 - ii. Treatment with anti-CD20 has been within 12 months prior to enrollment.
- g. Any prior treatment with cell-depleting therapies other than anti-CD20, including investigational agents, including but not limited to, CAMPATH®, anti-CD4, anti-CD5, anti-CD3, anti-CD19.
- h. Any prior treatment with chlorambucil, bone marrow transplantation, or total lymphoid irradiation.
- 8. Receipt of a live-attenuated vaccine within 3 months of study enrollment.
- 9. Concomitant malignancies or a history of malignancy, with the exception of adequately treated basal and squamous cell carcinoma of the skin, or carcinoma in situ of the cervix.
- 10. Major surgery (including joint surgery) within 8 weeks prior to enrollment.
- 11. History of solid organ or hematopoietic stem cell transplantation.
- 12. History of primary immunodeficiency.
- Comorbidities requiring systemic corticosteroid therapy, including those which have required three or more courses of systemic corticosteroids within the 12 months prior to enrollment.
- 14. Current substance abuse or history of substance abuse within 12 months prior to enrollment.
- 15. History of severe depression or severe psychiatric condition.
- 16. Lack of peripheral venous access.
- Known hypersensitivity to brentuximab vedotin, a component thereof, or the excipient contained in the drug formulation.
- 18. Severe, progressive, or uncontrolled renal, hepatic, hematological, gastrointestinal, pulmonary, cardiac, or neurological disease (or, in the investigator's opinion, any other concomitant medical condition that places the

participant at risk by participating in this study), including but not limited to:

- Uncompensated congestive heart failure (New York Heart Association Class III or VI).
- b. Clinically significant active coronary artery disease (e.g., unstable angina or acute myocardial infarction within 6 months prior to enrollment).
- Recently active cerebrovascular disease (e.g., stroke or transient ischemic attack within 6 months prior to enrollment).
- d. Uncontrolled systemic hypertension.
- e. Confirmed diagnosis of diabetes mellitus.
- f. Pancreatitis within 30 days prior to enrollment.
- g. History or presence of peripheral neuropathy, such as mononeuritis multiplex, acute or chronic inflammatory demyelinating polyneuropathy, axonal sensorimotor neuropathies, or drug related neuropathy or neuritis.

19. Evidence of infection:

- a. Any infected ulcer at enrollment.
- b. Active bacterial, viral, fungal, or opportunistic infections requiring systemic anti-infective therapy.
- c. Evidence of current or prior infection with tuberculosis
 - Positive QuantiFERON® TB Gold or TB Gold Plus test results. Purified protein derivative (PPD) tuberculin test may be substituted for QuantiFERON® – TB Gold or TB Gold Plus test.
 - ii. Indeterminant QuantiFERON® TB Gold or TB Gold Plus test results, unless followed by a subsequent negative PPD or negative QuantiFERON® and clearance by local Infectious Disease department.
- d. Evidence of current or prior infection with
 - i. Human immunodeficiency virus (HIV), or
 - ii. Hepatitis B (as assessed by hepatitis B surface antigen, HBsAg and antibody to hepatitis B core antigen, anti-HBc), or
 - iii. Hepatitis C (HCV), except adequately treated HCV with documentation of sustained

virologic response defined as undetectable HCV RNA at least 12 weeks after the end of treatment.

- e. History of progressive multifocal leukoencephalopathy (PML).
- f. Hospitalization for treatment of infections, or parenteral (intravenous or intramuscular) antibacterial, antivirals, anti-fungal, or anti-parasitic agents within the past 60 days prior to enrollment.
- g. Chronic infection that is currently being treated with systemic suppressive antibiotic or antiviral therapy, including but not limited to tuberculosis, pneumocystis, cytomegalovirus, herpes simplex virus, herpes zoster, and atypical mycobacteria.
- h. History of significant infection or recurrent infection that, in the investigator's opinion, places the participant at risk by participating in this study.
- i. Positive PCR test for SARS-CoV-2 within the two weeks prior to enrollment.
- 20. The following laboratory abnormalities:
 - a. Neutropenia (absolute neutrophil count <1500/mm³).
 - b. Thrombocytopenia (platelets <100,000/mm³).
 - c. Moderately severe anemia (hemoglobin, Hgb < 10 g/dL).
 - d. Liver function test (aspartate aminotransferase [AST], alanine aminotransferase [ALT], or alkaline phosphatase) results that are ≥ 1.5 times the upper limit of normal.
 - e. Serum total bilirubin > 1.5 times the upper limit of normal, or > 3 times the upper limit of normal in the presence of Gilbert's syndrome.
 - f. Serum amylase and serum lipase > 1.5 times the upper limit of normal.
- 21. Renal dysfunction, defined as either one of the following:
 - a. Serum creatinine > 1.5 times the upper limit of normal.
 - b. Estimated glomerular filtration rate (eGFR) < 60 mL/min/1.73m2.
- 22. Pregnancy.
- 23. Breastfeeding.

Immune Tolerance Network CONFIDENTIAL Page 17

- 24. Unwillingness to use two forms of medically acceptable contraception methods by participants and their partners (if of reproductive potential) during the study and for at least 6 months after last dose of study drug.
- 25. Inability to comply with study and follow-up procedures.

Immune Tolerance Network CONFIDENTIAL Page 18

ABBREVIATIONS

ABVD Doxorubicin, Bleomycin, Vinblastine, and Dacarbazine

AE Adverse Event

ALCL Anaplastic Large Cell Lymphoma

ALT Alanine Aminotransferase

ANA Anti-Nuclear Antibodies

ASCT Autologous Stem Cell Transplant

AST Aspartate Aminotransferase

BUN Blood Urea Nitrogen

CBC Complete Blood Count

CDC Centers for Disease Control and Prevention

CFR Code of Federal Regulations

CRISS Combined Response Index in Systemic Sclerosis

CRP C-Reactive Protein

CTCAE Common Terminology Criteria for Adverse Events

CYP3A4 Cytochrome P450 3A4

dcSSC Diffuse Cutaneous Systemic Sclerosis

DAIT Division of Allergy, Immunology, and Transplantation

DSC Discontinuation Visit

DLCO Diffusing Capacity of the Lung for Carbon Monoxide

DSMB Data and Safety Monitoring Board

eCRF Electronic Case Report Form

eGFR Estimated Glomerular Filtration Rate

EKG Electrocardiogram

ELISPOT Enzyme-linked Immunospot

ESR Erythrocyte Sedimentation Rate

FDA Food and Drug Administration

FEV1 Forced Expiratory Volume 1

FVC Forced Vital Capacity

GCP Good Clinical Practice

GVHD Graft Versus Host Disease

HBsAg Hepatitis B Surface Antigen

HBc Hepatitis B Core Antigen

HCG Human Chorionic Gonadotropin

HCV Hepatitis C Virus

HIV Human Immunodeficiency Virus

HRQOL Health-related quality of life

HL Hodgkin's lymphoma

IB Investigator's brochure

ICH International Conference on Harmonisation

ICOS Inducible Costimulator

IHC Immunohistochemistry

IND Investigational New Drug

IRB Institutional Review Board

ISH In Situ Hybridization

ITN Immune Tolerance Network

IVIG Intravenous Immunoglobulin

LLN Lower Limit of Normal

LVEF Left Ventricular Ejection Fraction

MedDRA Medical Dictionary for Regulatory Activities

MMAE Monomethyl Auristatin E

mRSS Modified Rodnan Skin Score

NCI National Cancer Institute

NIAID National Institute of Allergy and Infectious Diseases

NIH National Institutes of Health

NK Natural Killer

OHRP Office for Human Research Protections

OSHA Occupational Safety and Health Administration

PBMC Peripheral Blood Mononuclear Cell

PCR Polymerase Chain Reaction

PDE-5 Phosphodiesterase type 5

P-gp P-glycoprotein

PH Pulmonary Hypertension

PML Progressive Multifocal Leukoencephalopathy

PP Per Protocol

PPD Purified Protein Derivative

RA Rheumatoid Arthritis

REMS Risk Evaluation and Mitigation Strategy

RNA Ribonucleic Acid

SACCC Statistical and Clinical Coordinating Center

SAE Serious Adverse Event

SAR Serious Adverse Reaction

SARS-CoV-2 Severe Acute Respiratory Syndrome Coronavirus 2

SAP Statistical Analysis Plan

SAS Statistical Analysis System

SCID Severe Combined Immunodeficiency

SHAQ-DI Scleroderma Health Assessment Questionnaire-Disability

Index

SLE Systemic Lupus Erythematosus

SNP Single Nucleotide Polymorphisms

SOP Standard Operating Procedure

SSc Systemic Sclerosis

Safety Review Committee SRC

ULN Upper Limit of Normal

WHO World Health Organization

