5.1.3.4.3 Administration

Brentuximab vedotin or placebo will be administered as an intravenous infusion over approximately, but no less than, 30 minutes, as described in the prescribing information at study weeks 0 through 21. Hematology and serum chemistry results must be obtained within 72 hours prior to infusions at study weeks 3 through 21.

Brentuximab vedotin must not be administered as an intravenous (IV) push or bolus. Do not mix brentuximab vedotin, or administer as an infusion, with any other medicinal products. If an infusion related reaction occurs, the infusion should be interrupted and medical management instituted as needed (e.g., corticosteroids, epinephrine, bronchodilators, or oxygen). In cases of mild reactions (\leq Grade 2), the infusion can be resumed at a 50% rate reduction when symptoms have resolved and are no longer deemed a threat to the participant's well-being. If anaphylaxis occurs, immediately and permanently discontinue brentuximab vedotin and administer emergency medical therapy.

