5.2.4 Permanent Discontinuation of Study Medication for Toxicity

Permanently discontinue brentuximab vedotin if any of the following occurs:

- The participant misses > 3 doses of brentuximab vedotin.
- Grade 2 peripheral neuropathy recurs after brentuximab vedotin suspension and dose modification, as described above.
- Grade 3 or greater peripheral neuropathy.
- Grade 3 or greater neutropenia or thrombocytopenia.
- Grade 3 or greater infusion reaction.
- Anaphylaxis, defined as a serious allergic reaction that is rapid in onset and may cause death (see Appendix 2) [79].
- New onset rash consistent with Stevens-Johnson syndrome, toxic epidermal necrolysis, or other drug reaction.
- eGFR $< 30 \text{ ml/min}/1.73 \text{ m}^2$.
- Potential drug-induced liver injury, defined as all three of the following:
 - o ALT or AST elevation > 3 times upper limit of normal (ULN), and
 - Total bilirubin > 2 times ULN, without initial findings of cholestasis (elevated serum alkaline phosphatase), and
 - No other immediately apparent possible causes of ALT or AST elevation and hyperbilirubinemia, including but not limited to viral hepatitis, preexisting chronic or acute liver disease, or the administration of other drugs known to be hepatotoxic.
- Two or more Grade 3 or greater infections, or one Grade 4 infection.

• A suspected case of PML.

A diagnosis of PML should be considered in any participant presenting with new-onset or deteriorating neurological signs and symptoms. The participant should be referred to a neurologist or other appropriate specialist for evaluation. If PML is suspected, this should be immediately reported to the NIAID Medical Monitor. The appropriateness of continuing study medication, while the case is being assessed, should be discussed.

If brentuximab vedotin is discontinued, the procedures in Section 4.3 should be followed.

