8.5.2 Reporting of Serious Adverse Events and Events of Special Interest

This section describes the responsibilities of the site investigator to report serious adverse events and events of special interest to the sponsor via the electronic CRF (eCRF). Timely reporting of adverse events is required by 21 CFR Part 312.32, and ICH E6 guidelines.

The adverse events outlined below must be reported by the site investigators to DAIT/NIAID via the DAIT-SACCC regardless of relationship or expectedness to study intervention within 1 business day of discovery of the event:

- All SAEs per 21 CFR 312.32 definitions (see Section 8.2.4, Serious Adverse Events).
- The following events of special interest regardless of drug relationship:
 - o Grade 3 or higher peripheral neuropathy.
 - o Grade 3 or higher neutropenia or thrombocytopenia.
 - o Grade 3 or higher infusion reaction.
 - Anaphylaxis, defined as a serious allergic reaction that is rapid in onset and may cause death (see Appendix 2) [79].
 - New onset rash consistent with Stevens-Johnson syndrome, toxic epidermal necrolysis, or other drug reaction.

- $o = eGFR < 30 \text{ ml/min/1.73m}^2$.
- o Potential drug-induced liver injury, defined as all three of the following:
 - ALT or AST elevation > 3 times ULN, and
 - Total bilirubin > 2 times ULN, without initial findings of cholestasis (elevated serum alkaline phosphatase), and
 - No other immediately apparent possible causes of ALT or AST elevation and hyperbilirubinemia, including but not limited to viral hepatitis, pre-existing chronic or acute liver disease, or the administration of other drugs known to be hepatotoxic.
- o Grade 3 or greater infection.
- A suspected case of PML.
- All other Clinical events with an NCI-CTCAE Grade 3 or greater severity deemed possibly or definitely related to brentuximab vedotin.

Note: clinical events include signs/symptoms, diagnoses, and laboratory abnormalities with clinical consequence (defined as the requirement for intervention, correction, increased monitoring, or further evaluation).

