8.11.3 Ad hoc DSMB Reviews (Stopping Rule Guidance)

If any of the following events occur, the chair of the DSMB will be notified and a review of the safety data will be performed. The DSMB will have the discretion to recommend actions regarding study conduct, and will determine if enrollment in the study should be stopped and/or administration of investigational study medication should be halted:

- 1. Any death that is at least possibly related to use of the investigational study medication.
- 2. Any life-threatening infusion reactions during infusion of study medication or within the observation period after study medication that lead to permanent discontinuation of the infusion, including anaphylaxis.
- 3. One case of PML.
- 4. Any grade 4 adverse event that is at least possibly related to use of the investigational study medication.
- 5. Two or more Grade 3 or higher peripheral neuropathy events involving different participants.

If stopping rule 1, 2, or 3 is met, then no new participants will be consented, and no new participants will be enrolled, until after the DSMB completes review of the safety data. Participants in the screening phase of the study may continue to undergo minimal risk procedures.

If stopping rule 4 or 5 is met, the study will proceed as planned pending DSMB review of the data. However, if two weeks has elapsed and the DSMB has not met, then no new participants will be consented, and no new participants will be enrolled, until after the DSMB completes review of the safety data.

In the event that a temporary halt is placed on consent and enrollment, participants already enrolled in the study will continue to receive study medication if they are not the subject of the DSMB review.

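### Secondary safety endpoint 5d counts drug rash, including SJS and TEN, as an infusion reaction, so its rate cannot be assigned to either toxicity

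*Protocol*

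**What the plan says.** Endpoint 5 appears in the Protocol synopsis, in 3.4.2 and in 9.2.2. Its stem is "The proportion of participants with any of the following Grade 3 or higher adverse events at or before week 48", followed by items a to e: peripheral neuropathy, neutropenia, infectious events, item d and PML. Item d is "Infusion reactions, including anaphylaxis and new onset rash consistent with Stevens-Johnson syndrome, toxic epidermal necrolysis, or other drug reaction". It sets no time limit relative to an infusion; the only horizon is week 48.

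Other sections keep these events apart:

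- Section 5.2.4 (permanent discontinuation) lists "Grade 3 or greater infusion reaction" as one item. Anaphylaxis and new-onset drug rash are further items.
- Section 8.5.2 (events of special interest) does the same, with "Grade 3 or higher infusion reaction" and, as a separate entry, "New onset rash consistent with Stevens-Johnson syndrome, toxic epidermal necrolysis, or other drug reaction".
- Section 1.4.1 names SJS and TEN separately from the paired warning for anaphylaxis and infusion reactions.
- Section 1.4.1.4 reports Grade 1 or 2 infusion reactions in 12% of participants in the pivotal phase II trials. SJS and TEN come in another paragraph, as rare but fatal and serious reactions.

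Section 9.2.2 analyses the different types of adverse events in the same way as the primary endpoint: Clopper-Pearson intervals by treatment group and Fisher's exact test within each cohort. Section 9.2.3 adds an exact Cochran-Armitage trend test and logistic regression over the four dose levels.

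**The concern.** Endpoint 5 is where the trial reports its named severe toxicities by dose. An infusion reaction is tied to the act of infusing. Section 5.1.3.4.3 says "If an infusion related reaction occurs, the infusion should be interrupted and medical management instituted as needed", and stopping rule 2 in 8.11.3 refers to the infusion and the observation period after it. A drug rash need not have that timing. Under 5d, a Grade 3 rash well after an infusion still enters the infusion-reaction count. So does a rash in the 27-week follow-up phase, when no infusion is planned.

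A reader of the results could take a non-zero 5d rate, or a trend in it across doses, as evidence about infusion tolerability when all of it came from skin toxicity. The reverse error is equally possible. The document treats the two as separate risks, and safety and tolerability are the primary objective.

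**Working it through.** **Inputs.** Each cohort has 6 active and 2 placebo participants (9.3). The interval method is exact 95% Clopper-Pearson (9.2.1). The event counts below are assumed, to show how the definition behaves. They are not forecasts.

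**Step 1: reproduce the plan's figures.** For x = 0 of n = 6 the lower limit is 0 and the upper limit is 1 − 0.025^(1/6) = 0.459. For x = 1 the lower limit is 1 − 0.975^(1/6) = 0.004, and the upper limit solves (1 − p)^6 + 6p(1 − p)^5 = 0.025, giving p = 0.641. For x = 2 the limits are 0.043 and 0.777. All agree with Table 3 in 9.3, and the other rows of that table also reproduce.

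**Step 2: apply 5d as written and after a split.**

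| Assumed events in one active cohort | 5d as written | Infusion reactions alone | Drug rash alone |
|---|---|---|---|
| One delayed Grade 3 drug rash | 1/6 = 16.7% (0.4% to 64.1%) | 0/6 (0% to 45.9%) | 1/6 = 16.7% (0.4% to 64.1%) |
| One Grade 3 infusion reaction and one Grade 3 drug rash, different participants | 2/6 = 33.3% (4.3% to 77.7%) | 1/6 = 16.7% (0.4% to 64.1%) | 1/6 = 16.7% (0.4% to 64.1%) |

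One misfiled event moves the rate by 1/6, or 16.7 percentage points.

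**Step 3: effect on the tests.** Fisher's test against 0/2 placebo does not change. With one event among 8 participants, the chance that it falls on an active participant is 6/8 = 0.75. With two events, the chance that both do is C(6,2)/C(8,2) = 15/28 = 0.54. In each case this is the most probable table, so the two-sided p is 1.0; with no events it is also 1.0. The harm therefore lies in what the rate, interval and trend are taken to measure. No significance result is reversed within a cohort.

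**Step 4: timing.** Treatment runs to week 21 and the endpoint to week 48. That leaves 48 − 21 = 27 weeks in which a rash would still be counted in 5d with no infusion scheduled.

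**The case against.** Several points against the concern have force.

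- **Anaphylaxis belongs where it is.** Section 1.4.1 pairs it with infusion reactions, 5.1.3.4.3 handles it in the infusion paragraph, and stopping rule 2 in 8.11.3 includes it among them. This stands, and the point is confined to rash.
- **Infusion reactions can appear later.** Section 5.1.3.4.1 allows for reactions during or following administration, and 1.4.1.4 covers infusion reactions and skin disorders under one heading. This softens the boundary, but it does not turn a rash weeks later into an infusion reaction.
- **The item may mean only rash that arises as an infusion reaction.** Then a later SJS or TEN would have no named place in endpoint 5. A split settles that as well.
- **Rash from background immunosuppressants would be counted.** This is true, but 8.4.3 records events regardless of relationship, so it applies to every adverse-event endpoint and is not a fault of 5d.
- **Endpoint 5 may be a single composite.** The stem permits that reading, and under it the split changes nothing. The wording of 9.2.2 on the different types of adverse events points towards separate rates.
- **The events are visible elsewhere.** Section 9.2.6 codes adverse-event displays in MedDRA, and secondary endpoint 2 counts all Grade 2 or higher events. This limits the harm considerably.

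A reader might also infer that the Grade 3 floor is an error, because 5.2.4 has "A suspected case of PML" and 8.11.3 has "One case of PML", both ungraded, so that PML could pause enrolment while endpoint 5 shows none. The documents do not support this. Discontinuation and reporting triggers may reasonably be more sensitive than a severity-graded endpoint. The contradiction would also need a PML case graded 1 or 2. Section 1.4.1.2 puts any PML below 0.05% in treated cancer patients; if that rate applied to the 18 planned active participants, the chance of any case would be below 1 − 0.9995^18 = 0.9%. Counting PML by 8.5.2 would also bring in suspected cases later ruled out, and would still differ from the stopping rule.

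**Conclusion.** The misclassification is real and minor. The document contradicts its own event lists by placing drug rash inside infusion reactions, and in a cohort of 6 one such event turns 0/6 into 1/6 under the wrong label. This assumes that 5d is reported as its own rate and that a delayed rash is counted there, as the text says. The effect is on the interpretation of one secondary endpoint in a study that 9.3 describes as exploratory. The Grade 3 threshold and the PML item can stay as they are.

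**What to change.** In the synopsis, 3.4.2 and 9.2.2, replace item d with two items under the existing stem:

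1. Grade 3 or higher infusion reactions, including anaphylaxis.
2. Grade 3 or higher new-onset rash consistent with SJS, TEN or other drug reaction.

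Report each with its own rate, interval and trend analysis. Optionally, add a descriptive count of all rash events that meet 8.5.2 at any grade, since sites must already report them within one business day.

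The cost is a wording change in three places and one or two more table rows, with sparse counts. No new data are needed and no clinical rule changes.
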